2.2 SCREENING EVALUATION

Note: Screening evaluation testing/procedures are conducted under the separate screening protocol 06C0014 OR the consent for study 01C0129 (provided the procedure is permitted on that study) per PI discretion. Assessments and procedures to confirm study eligibility should be completed as follows:

Within 4 Weeks Prior to Protocol Enrollment:

- a. Medical history and physical exam including vital signs and performance status.
- b. Confirmation of histology (archival or fresh tissue if archival tissue is insufficient), PD-L1 expression and mutation status (EGFR and ALK) by the Laboratory of Pathology (any time prior to enrollment). This confirmation will be done under protocol 06C0014 (patients will be co-enrolled).
- c. Blood tests:
 - i. CBC with differential
 - ii. Acute Care Panel: Sodium, potassium, chloride, bicarbonate, creatinine, glucose, BUN, eGFR
 - iii. Hepatic Panel: Alkaline phosphatase, ALT, AST, total and direct bilirubin
 - iv. PT/PTT
- d. Viral Markers (anti-HIV, anti-HCV, HBsAg, anti-HAV IgM); HCV RNA if needed.
- e. 12-lead EKG. Patients with EKG evidence of cardiac ischemia (ST depression/elevation greater than or equal to 2 mm), or arrhythmia will undergo cardiology evaluation to determine eligibility.
- f. Echocardiogram
- g. X-rays, contrast enhanced CT scans of chest, abdomen, pelvis, as well as brain MR, and fused PET-CT scans to evaluate the status of disease (all imaging must be obtained within 4 weeks prior to starting therapy).
- h. Pulmonary function tests (PFTs) with and/or without bronchodilators.
- i. Arterial Blood Gas test (ABG) on room air (to be drawn if pulse oximetry < 90% on room air).
- j. Lupus Anticoagulant and ANA

Within 3 Days Prior to Protocol Enrollment:

a. Women of child-bearing potential will have a urine or serum β hCG pregnancy test.

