3 STUDY IMPLEMENTATION

3.1 STUDY DESIGN

This trial is unique in that it is intended to establish the rationale and conditions for the use of oral DAC-THU and pembrolizumab therapy for NSCLC, EsC, and MPM. The goal is to establish the basis for subsequent evaluation of this treatment regimen in combination with other agents targeting MDSC, or adoptive immunotherapy regimens in patients with thoracic malignancies.

Patients potentially eligible for trial will be evaluated, and undergo subsequent eligibility assessment in the Thoracic Surgery Clinic/NCI. Patients meeting eligibility criteria will undergo baseline (if fresh tumor biopsy was not performed at screening) and post treatment tumor biopsies either by percutaneous image-guided FNA techniques in Interventional Radiology (Clinical Center/NIH) or endoscopic/thoracoscopic techniques in the CC operating room by Thoracic Surgery staff using standard of care practice guidelines. Tumor biopsies may be omitted at the discretion of the PI if risks outweigh potential research benefits.

The Phase I component will be a standard 3+3 design starting with oral DAC-THU on two consecutive days (preferably Tuesday and Wednesday) for two weeks out of three weeks for 9

weeks with incremental dose escalation as shown in Section **3.1.3**. Patients with high PD-L1 tumor expression will be combined with patients with low PD-L1 tumor expression to minimize accrual numbers required for the Phase I component of the study. Pembrolizumab will be administered on Wednesday, Thursday or Friday at a fixed intravenous dose of 200 mg q 3 weeks. One cycle is three weeks; one course is 9 weeks. Treatment evaluation including repeat tumor biopsy will be performed after one course of therapy (Week 10 +/- one week). Those patients exhibiting disease progression or unacceptable toxicities will be removed from study. Patients exhibiting stable disease or disease regression will be offered an additional course of therapy followed by treatment evaluation (without mandatory biopsy). Treatment will continue in this manner until off-study criteria have been met.

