3.3.1 General Guidance for Dose Modifications

- 3.3.1.1 Patients may continue to receive therapy provided the following criteria are met on Day 1 of each cycle:
 - Non-hematologic toxicity recovered to < Grade 2 (or tolerable Grade 2 or baseline).
 - No evidence of progressive disease.
- 3.3.1.2 In the event of an adverse event at least possibly related to the investigational agent, the dose of the investigational agent should be adjusted according to the parameters articulated above and guidelines listed in the Dose Delays / Dose Modifications tables shown below (**Table 9** and **Table 10**). If an adverse event is not covered in such tables, doses may be held at the discretion of the investigator for the subject's safety.

3.3.1.3 If patients fail to recover to CTCAE Grade 0-1, tolerable Grade 2 (or within 1 grade of starting values for pre-existing laboratory abnormalities), or baseline from a treatment-related adverse event attributable to DAC-THU within 42 days (2 cycles), they cannot receive additional DAC-THU. Patients may continue pembrolizumab monotherapy at the investigator discretion provided that discontinuation criteria for pembrolizumab toxicity have not been met.

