3.4 ON STUDY PROTOCOL EVALUATION (APPENDIX 3: STUDY CALENDAR)

3.4.1 Baseline Assessments

Note: Baseline assessments do not need to be repeated if performed during screening in the designated time frame.

Any Time Prior to Initiation of Treatment:

- a. HLA class I and class II analysis of PBMC.
- b. Tumor biopsy if fresh sample from previous biopsy is not available. Note: Samples collected on 06C0014 or any other NCI protocol in which the patient is co-enrolled can be used.

Within 10 Days Prior to Commencing DAC-THU/Pembrolizumab Therapy:

- a. Physical examination including assessment of vital signs and ECOG status.
- b. Chemistries
 - i. Acute Care Panel Sodium (Na), Potassium (K), Chloride (Cl), Total CO2 (bicarbonate), Creatinine, Glucose, Urea nitrogen (BUN),
 - ii. Mineral Panel Albumin, Calcium total, Magnesium total (Mg), Phosphorus
 - iii. Hepatic Panel Alkaline Phosphatase, ALT/GPT, AST/GOT, Total Bilirubin, Direct Bilirubin
 - iv. LD, Total Protein, Total CK, Uric Acid
- c. Fetal hemoglobin
- d. CBC, differential, platelet count, PT, PTT
- e. T, B, NK cell subsets
- f. Urinalysis and culture if indicated
- g. Pulmonary Function Test
- h. Arterial Blood Gas on room air (to be drawn if pulse oximetry <90% on room air).
- i. Research Labs (refer to Appendix 4 for details).

Within 48 Hours Prior to Initiation of DAC-THU/Pembrolizumab Therapy:

a. Women of child-bearing potential will have a urine or serum βhCG pregnancy test.

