3.4.2 Treatment Evaluation

Twice Weekly During First Course of Therapy, and Weekly Thereafter Unless Clinically Indicated:

- a. CBC with differential
- b. Sodium (Na), Potassium (K), Chloride (Cl), Total CO2 (bicarbonate), Creatinine, Glucose, Urea nitrogen (BUN), Albumin, Calcium total, Magnesium total (Mg), Phosphorus, Alkaline Phosphatase, ALT/GPT, AST/GOT, Total Bilirubin, Direct Bilirubin, LD, Total Protein, Total CK, Uric Acid
- c. PT/PTT

Note: The patient may have lab work obtained through his or her local physician.

Every Three Weeks During Therapy:

a. T, B, NK cell subsets

Performed After Each Course:

- a. Physical examination including assessment of vital signs and ECOG status.
- b. Sodium (Na), Potassium (K), Chloride (Cl), Total CO2 (bicarbonate), Creatinine, Glucose, Urea nitrogen (BUN), Albumin, Calcium total, Magnesium total (Mg), Phosphorus, Alkaline Phosphatase, ALT/GPT, AST/GOT, Total Bilirubin, Direct Bilirubin, LD, Total Protein, Total CK, Uric Acid
- c. CBC, differential, platelet count, PT, PTT
- d. Thyroid Function Tests
- e. T, B, NK cell subsets
- f. Urinalysis and culture if indicated
- g. Biopsy of index lesion (only on first treatment evaluation).

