3.4.4 Follow-Up Evaluations

Patients who are removed from treatment due to disease progression or unacceptable, dose-limiting toxicities or who voluntarily withdraw from treatment will be monitored weekly until treatment related toxicities have resolved to baseline at which time they will be removed from study.

Toxicity Evaluation:

 Laboratory evaluation: CBC, Chemistries (Sodium, potassium, chloride, bicarbonate, creatinine, glucose, BUN, albumin, total calcium, ionized calcium, magnesium, phosphorus, alkaline phosphatase, ALT/SGPT, AST/SGOT, total bilirubin, direct bilirubin, lactate dehydrogenase, total protein, creatine kinase, uric acid), PT/PTT

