4. *Teratogenicity:* Pre-clinical data indicates that there is a teratogenic risk even at low doses of decitabine. Therefore, all clinical studies with decitabine must take into account, and incorporate precautions, to address a risk for teratogenicity. Current standard therapy for SCD with either HU or stem cell transplantation also has teratogenic risks (pregnancy category D).

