15.2.3 Appendix 3: Study Calendar

Screening to Completion of DAC-THU/Pembrolizumab

				istered only	regression	Onwards]* ho exhibit stable disease	
Procedure	Screening Within 4 weeks prior to enrollment	Baseline Within 10 days prior to start of DAC- THU	During T Day 1 of DAC- THU	Treatment Day 2 of DAC- THU	Within 3 days prior to completion of DAC- THU	At the end of course completion	End of Treatment Visit ⁷
History and PE	Х	X				Х	Х
Vital signs	Х	X				Х	Х
Performance Score	Х	X				Х	
NCI LP Confirmation of Dx ¹	Х						
CBC with differential; Acute Care Panel, Hepatic Panel (Sections 2.2 and 3.4.1)	Х	Х			ng Course 1, ess clinically d	Х	Х
PT, PTT	Х	X			ng Course 1, ess clinically d	Х	
Thyroid Function Tests						Х	
Albumin, Ca ²⁺ total, Mg ²⁺ total, Phosphorus, LD, Total Protein, Total CK, Uric Acid		X			ng Course 1, ess clinically d	Х	Х
Fetal Hemoglobin		X					
Urinalysis		X4				X^4	
Anti HIV, anti HCV, HBsAg, anti-HAV IgM, and if needed, HCV RNA	Х						
Urine or serum HCG in women of childbearing potential	X ³	X ³					
T, B, NK cell subsets		X9				Х	

				stered only	I+1 [Course 2 for patients we regression	Onwards]* ho exhibit stable disease	
	Screening Within 4 weeks	Baseline Within 10 days prior to start of DAC-	Day 1 of DAC-	Treatment Day 2 of DAC-	Within 3 days prior to completion of DAC-	At the end of course completion	End of Treatment
Procedure	prior to enrollment	THU	THU	THU	THU		Visit ⁷
HLA class I and class II analysis of PBMC	\mathbf{X}^1						
EKG	Х						
Echocardiogram	Х						
PFTs	Х	X					
ABGs (to be drawn if pulse oximetry <90% on room air)	Х	X					
Lupus Anticoagulant and ANA	Х						
Radiological Assessments	\mathbf{X}^2					X^2	
DAC-THU			Once a d	ay on days dose lev	according to el		
Tumor sample for research ⁸		Х				Х	
Correlative Research Studies		X ⁵	X ⁵		X ⁵		
PK/PD			X6	X6			
Adverse Events ¹⁰			х —			→	
Concomitant Medications ¹⁰		X				→	

^{1.} May be obtained any time prior to initiation of study therapy. Does not need to be repeated if already done at NCI.

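### No pregnancy test is scheduled after the first dose, although the protocol states a teratogenic risk at low decitabine doses and 12-dose courses repeat without a fixed limit

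*Combined protocol and SAP*

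**What the plan says.** Pregnancy testing appears in three places.

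- Section 2.2 lists a urine or serum test under "Within 3 Days Prior to Protocol Enrollment".
- Section 3.4.1 lists one under "Within 48 Hours Prior to Initiation of DAC-THU/Pembrolizumab Therapy".
- The Appendix 3 row "Urine or serum HCG in women of childbearing potential" is marked under Screening and Baseline. Its footnote 3 gives the same two windows.

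Section 3.1 says of the repeating 9-week courses: "Treatment will continue in this manner until off-study criteria have been met". Section 13.1.9 says: "Pre-clinical data indicates that there is a teratogenic risk even at low doses of decitabine". It adds that decitabine studies have to build in precautions against that risk.

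The protocol does contain precautions. Section 2.1.1.16 requires two contraceptive methods, one of them highly effective, until 60 days after treatment, and obliges a participant to report a known or suspected pregnancy at once. Section 2.1.2.6 excludes pregnant women. Sections 3.6.1 and 8.5.1 stop treatment immediately if a patient becomes pregnant, and Section 8.5.1 requires a report to the sponsor within 24 hours.

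**The concern.** The stopping rule for pregnancy works only once the pregnancy is known, and after the first dose no scheduled assessment is designed to find one. If contraception fails and the patient does not suspect it, the next course can start without a check. Suspicion may also be weaker than usual here: Section 13.1.9 lists fatigue and nausea among decitabine's common side effects, so early symptoms of pregnancy could be put down to treatment.

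What is at stake is patient and fetal safety. The response endpoints, dose finding, sample size and error rates are untouched.

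**Working it through.** **1. Is any test scheduled after the first dose?** The plan gives no figure to reproduce, so the places where a test could stand are set side by side.

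| Place in the protocol | Pregnancy test listed? |
|---|---|
| 2.2, screening | Yes, before enrollment |
| 3.4.1, baseline | Yes, before first dose |
| 3.3.1.1, introduced by "Patients may continue to receive therapy provided the following criteria are met on Day 1 of each cycle" | No |
| 3.4.2, twice-weekly/weekly and three-weekly lists | No |
| 3.4.2, "Performed After Each Course" | No |
| 3.4.4, "Laboratory evaluation: CBC, Chemistries" and the items that follow | No |
| Appendix 3, hCG row, columns after Baseline | No marks |
| Appendix 4, research samples | No |

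The result is at most two scheduled tests before the first dose and none after it.

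The calendar table is partly broken in the text as read, and a Baseline mark there need not mean baseline only: the T, B, NK subset row is marked at Baseline with a footnote meaning every three weeks. The finding therefore rests mainly on calendar footnote 3 and on Sections 2.2, 3.4.1, 3.4.2 and 3.4.4, which all agree.

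**2. How many doses fall in one course?** Table 7 (Section 3.1.3) gives dosing on two days in weeks 1, 2, 4, 5, 7 and 8.

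- DAC-THU doses per course: 6 weeks × 2 days = 12.
- DAC-THU doses per three-week cycle: 2 weeks × 2 days = 4.
- Pembrolizumab infusions per course: 9 weeks / 3 weeks = 3.

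Check against Table 7's course totals:

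- THU: 120 / 10 = 12.0 doses.
- DAC, level −1: 12 × 0.17 = 2.04 mg/kg, stated as 2.0.
- DAC, level 1: 12 × 0.21 = 2.52 mg/kg, stated as 2.5.
- DAC, level 2: 12 × 0.25 = 3.00 mg/kg, stated as 3.0.

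The differences are rounding, so 12 doses per course is confirmed.

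**3. How many doses pass since the last scheduled test?** With no doses held, the count after N completed courses under the current plan is 12 × N.

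| Completed courses | Weeks on treatment (9 × N) | Current plan | With a test after each course | With a test every three weeks |
|---|---|---|---|---|
| 1 | 9 | 12 | at most 12 | at most 4 |
| 2 | 18 | 24 | at most 12 | at most 4 |
| 3 | 27 | 36 | at most 12 | at most 4 |

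The last two columns give the largest number of doses between consecutive scheduled tests, whatever the number of courses. A test after each course does not shorten the untested interval within Course 1.

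**The case against.** The strongest reply is that this is a choice of monitoring intensity and breaks no rule of the protocol. Section 13.1.9 asks for precautions without naming on-treatment tests, and the protocol supplies several. Contact is also frequent: laboratory work twice weekly in Course 1 and weekly afterwards, pembrolizumab every three weeks, adverse event review weekly or every three weeks, and a history and examination at the end of each course. Any of these could bring out a missed period or a lapse in contraception and prompt an unscheduled test.

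The reply continues that 12, 24 and 36 count doses and do not measure risk. For fetal exposure to approach 24 or 36 doses, a pregnancy would have to begin near the start of treatment and go unnoticed for about 18 or 27 weeks. The remedy is also partial: it leaves Course 1 as it is, only patients with stable disease or regression go on to Course 2, and a conception early in a later course could still be exposed to most of that course's doses.

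Much of this stands. The safeguards are real, the dose counts are scheduling counts only, and the gain is limited to patients who continue beyond Course 1. What does not follow is that the existing contacts replace a test. Contraception can fail, self-report depends on suspicion, and neither an adverse event review nor a history and examination is a pregnancy screen.

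**Conclusion.** The concern holds as a low-cost safety improvement, worth considering at the next amendment. No pregnancy test is scheduled after the first dose, and the interval since the last scheduled test grows by 12 DAC-THU doses and 3 pembrolizumab infusions with every completed course. A test after each course would cap the interval at 12 doses.

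The counts assume full dosing with no holds. The likelihood of an undetected pregnancy cannot be computed from the documents, because the number of women of child-bearing potential is not given. The only bound is the accrual ceiling of 85 patients in Section 10; the true number is assumed to be small. The absence of a scheduled test is certain. Its practical consequence is probably rare but would be serious, and it has no bearing on the trial's estimates or decisions.

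**What to change.** 1. In Section 3.4.2, add a urine or serum hCG test for women of child-bearing potential to the after-course list, and require a negative result before the next course starts.
2. In Appendix 3, mark the hCG row in the end-of-course column.
3. Mark it conditionally at the End of Treatment visit, about 30 days after the last dose: test when the visit is in person or local laboratory work is drawn. Footnote 7 allows a remote visit, and the test would not be required then. This test comes too late to prevent dosing; it serves only detection and follow-up.

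Taking the end-of-course sample before the repeat CT and PET/CT scans would also cover the radiation exposure described in Section 11.4.1.8. Local radiology practice may already do this, but the documents do not say.

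The cost is one line of text and two calendar marks, one of them conditional. In practice it is one extra test per course in a probably small subgroup, on urine or on blood already drawn at that assessment, with a possible short delay if a result has to be repeated. Testing every three weeks would lower the maximum to 4 doses and would help within Course 1, at more burden. Testing per course is the lighter choice.

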15.2.4 Appendix 4: Pharmacokinetic Samples and Research Bloods

15.2.4.1 Course 1 Cycle 1

TEL Research Sample # (2 red top tubes, 2 lavender top tubes)	Immune Subset & CTC Samples # (2 CPT tubes, and 2 lavender top tubes)	# (1 6 mL groon ton	Hour (pre dose = within 1 hour prior to THU)	Target Time	Actual Time	Initials
Baseline (post - enrollment)						
R1	T1	n/a	n/a	n/a	n/a	n/a
Day 1 DAC-THU						
R2 (within 1 hour prior to THU)	T2 (within 1 hour prior to THU)	РК 1	pre dose			
n/a	n/a	РК 2	0.5h post DAC dose			
n/a	n/a	РК 3	1h post DAC dose			
n/a	n/a	РК 4	1.5h post DAC dose			
n/a	n/a	РК 5	2h post DAC dose			
n/a	n/a	PK 6	3h post DAC dose			
n/a	n/a	РК 7	4h post DAC dose			
n/a	n/a	PK 8	8h post DAC dose			
Day 2 DAC-THU						
n/a	n/a	РК 9	pre dose			
n/a	n/a	PK 10	0.5h post DAC dose			
n/a	n/a	PK 11	1h post DAC dose			
n/a	n/a	РК 12	1.5h post DAC dose			
n/a	n/a	РК 13	2h post DAC dose			
n/a	n/a	PK 14	3h post DAC dose			
n/a	n/a	РК 15	4h post DAC dose			
n/a	n/a	PK 16	8h post DAC dose			

After completion of each course of DAC- THU						
R3	Т3	n/a	n/a	n/a	n/a	n/a

15.2.4.2 Course N+1 (Course 2 Onwards)*

TEL Research Sample # (2 red top tubes, 2 lavender top tubes)	Immune Subset & CTC Samples # (2 CPT tubes, and 2 lavender top tubes)	(16 mL green ton	Hour (pre dose = within 1 hour prior to THU)	Target Time	Actual Time	Initials
Day 1 DAC-THU						
R4 * (within 1 hour prior to THU)	T4* (within 1 hour prior to THU)	n/a	pre dose			
After completion of each course of DAC- THU						
R5*	T5*	n/a	n/a	n/a	n/a	n/a

*Note: Labels should list the specific collection number as appropriate; indicated collection numbers are for Course # (e.g., Course 2) draws.

15.2.4.3 Instructions

PK Studies (PK)

Collect 6 mL blood in 1 green top tube. Tubes should then be placed on crushed ice, and samples should be centrifuged for 15 minutes at approximately_1000 x g at 0-5 °C within 2 hours after collection. The plasma should be transferred to separate pre-labeled screw-capped polypropylene transfer tubes and stored at -80 °C in the Thoracic Epigenetics Lab (TEL) until batched and later sent to the [name] Lab on dry ice for analysis.

Note: All samples are to be placed on wet ice and transported to the Thoracic Epigenetics Lab (TEL) within one hour of draw.

Research Labs (R)

Samples will be collected in 2 red top (10 mL each) tubes, and 2 lavender top tubes (EDTA; 10 mL each) for focused methylation analysis and immune response to treatment (see Section 5.1.2).

Note: All samples are to be placed on wet ice and transported to the Thoracic Epigenetics Lab (TEL) within one hour of draw.

Research Labs will be collected at the following timepoints (see also Appendix 3: Study Calendar):

- Baseline (once), see Section **3.4.1**;
- Each Course
 - Prior to DAC-THU initiation, and at

• DAC-THU completion.

Immune Subset and Circulating Tumor Cell Analysis (T)

Samples will be collected in 2 CPT citrate tubes (BD; 8 mL) for immune subset analysis (see Section 5.1.3) and 2 lavender top tubes (10 mL) for CTCs analysis (Section 5.1.4). The [name] Lab will be notified to pick up the samples (as indicated in Section 5.2.4) as soon as the blood is drawn for sample processing and analysis.

Samples will be drawn at the following timepoints (see also Appendix 3):

- Each course
 - Prior to DAC-THU initiation,
 - and at
 - DAC-THU completion.

Labeling (PK and Research Labs)

Prior to the infusion, the PK /research lab sheet and labels will be placed in the patient's room and a separate set of labels will be given to the Thoracic Epigenetics Lab staff. The labels will list the patient identifiers as well as the Cycle and draw number as appropriate. As the RN (or designee) draws the bloods, the RN (or designee) will place a label on the tube and write the sample reference # on the label on the tube. When the Thoracic Epigenetics Lab personnel or fellow processes the sample, the TEL personnel will label the storage tube with the label and will transcribe the corresponding sample reference # on the label on the tube.

Tracking (PK and Research Labs)

Upon completion of the PK/Research sample draws, the research nurse will make 3 copies of the PK sheet. The original and one copy should be placed in the research binder. 2 copies should be given to the TEL personnel. TEL will retain one copy for their records and will send the other copy with the PK samples to the [name] Lab. Note: Prior to sending the PK sheets to the [name] Lab, the patient name should be crossed out.
